2.1.1. Primary Estimand

The hematologic response at Week 12 in the target population:

- Population: Japanese participants with moderate and above aplastic anemia who are at least 2 years of age.*
- Variable: Hematologic response at Week 12.*
- Intercurrent events:*

The efficacy will be evaluated individually for each patient. Therefore, any missing data will not be imputed. All observations after prohibited concomitant medication will be included. Improvement in counts that are dependent upon exogenously administered growth factors or transfusion will not be considered as fulfilling hematologic response criteria in the evaluation.*

* Dependence upon exogenously administered growth factors or transfusion will be evaluated for each hematological test value (absolute neutrophil count, platelet count and reticulocyte count). When improvement in hematological test value is judged to be dependent upon growth factors or transfusion, it will not be considered as fulfilling the criteria described in section 3.1, regardless of the test values.

- Population-level summary: Due to the limited sample size, summary statistics will not be shown.*

2.1.2. Secondary Estimand(s)

The secondary estimand in this study is as follows:

- Population: Japanese participants with moderate and above aplastic anemia who are at least 2 years of age*
- Variable: Each secondary endpoint*
- Intercurrent events: The efficacy will be evaluated individually for each patient. Therefore, any missing data will not be imputed. All observations after prohibited concomitant medication will be included.*

As for the hematologic response at Week 24, improvement in counts that are dependent upon exogenously administered growth factors or transfusion will not be considered as fulfilling hematologic response criteria in the evaluation*.

* Dependence upon exogenously administered growth factors or transfusion will be evaluated for each hematological test value (absolute neutrophil count, platelet count and reticulocyte count). When improvement in hematological test value is judged to be dependent upon growth factors or transfusion, it will not be considered as fulfilling the criteria described in section 3.1, regardless of the test values.

- *Population-level summary: Due to the limited sample size, summary statistics will not be shown.*

[figure not shown]
2.1.3. Additional Estimand(s)

N/A.

2.2. Study Design

Study B5411003 will assess the efficacy and safety of PF-06462700 in participants with moderate and above aplastic anemia. This is a multicenter, open-label, single-arm study. The study will have a maximum duration of approximately 28 weeks. This includes an up to 4-week screening period, a 4-day treatment period and a 24-week follow-up period. This study will enroll the minimum of 3 participants. The study will be initially conducted at 3 sites. It is acceptable to assign to investigational product more than 3 subjects. The target sample size was determined based on the study feasibility perspective.

Figure 1. Study Design

3. ENDPOINTS AND BASELINE VARIABLES: DEFINITIONS AND CONVENTIONS

3.1. Primary Endpoint

Hematologic response at Week 12.

“Effective” when 2 or more of the following criteria are met:

- *Absolute neutrophil count $\geq 500/\mu\text{L}$.*
- *Platelet count $\geq 20,000/\mu\text{L}$.*
- *Reticulocyte count $\geq 60,000/\mu\text{L}$.*

Improvement in counts that are dependent upon exogenously administered growth factors or transfusion will not be considered as fulfilling response criteria.

For subjects of Stage 2b or 3 (see [Appendix 1](#)) at the baseline, hematological response will be “effective” when 2 or more of the above-mentioned criteria are met, and Stage is improved at the same time. (*If the baseline assessment is omitted, severity at the screening will be referred.)*

3.2. Secondary Endpoint(s)

3.2.1. Hematological response at Week 24

Hematological response described in [Section 3.1](#) will also be evaluated at Week 24.

3.2.2. Hematological test values

Hematological test values (absolute neutrophil count, platelet count and reticulocyte count) will be evaluated at Weeks 12 and 24. These values will also be evaluated at Day 4 and at Weeks 1, 2, 4, 6, 8 and 10. In case of early termination (ET), these values will be evaluated at ET and follow-up for ET.

As described in Schedule of Activities (SoA) section of the protocol, *Hematology test on Day 1 (baseline) can be omitted, if the interval between Screening visit and Day 1 visit is within 7 days.* In such cases, the values on screening visit will be used as baseline values.

3.2.3. Transfusion independence

Transfusion independence will be evaluated at Weeks 12 and 24.

The transfusion independence will be evaluated every 12 weeks. Participants who do not have any transfusion records from the time of the first dose of the investigational product at Day 1* to the day of Week 12 visit (inclusive) will be regarded as transfusion independent at Week 12. Participants who do not have any transfusion records from the day after Week 12 visit to Week 24 visit (inclusive) will be regarded as transfusion independent at Week 24. As for transfusion independence at baseline, participants who do not have any transfusion records from 84 days before Day 1 visit (inclusive) to the time of the first dose of the investigational product at Day 1* will be regarded as transfusion independent at baseline.

* If the time of the first dose of the investigational product or time of transfusion at Day 1 visit are not available, transfusion at Day 1 will contribute to transfusion dependence at Week 12 but not at baseline.

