1.2. Schema

1.3. Schedule of Activities (SoA)

The SoA table provides an overview of the protocol visits and procedures. Refer to the **STUDY ASSESSMENTS AND PROCEDURES** section of the protocol for detailed information on each procedure and assessment required for compliance with the protocol.

The investigator may schedule visits (unplanned visits) in addition to those listed in the SoA table, in order to conduct evaluations or assessments required to protect the well-being of the participant.

	Screening period	Treatment period				Follow-up period								Follow-up of ET case
		Day 1 ^a (baseline)	Day 2	Day 3	Day 4	Day 8 Week 1	Day 15 Week 2	Day 29 Week 4	Day 43 Week 6	Day 57 Week 8	Day 71 Week 10	Day 85 Week 12	Day 169 Week 24 or ET	
Visit Identifier ^a	Screening													Follow up 28 days after ET
Visit Window	Day -28 to -1	N/A	N/A	N/A	N/A	±1 day	±1 day	±3 days	±3 days	±3 days	±3 days	±7 days	±7 days	+7 days
Informed consent/assent	X													
Medical history	X													
Physical examination	X	X			X	X	X	X	X	X	X	X	X	
Vital signs	X	X	X	X	X	X	X	X	X	X	X	X	X	
Weight		X ^c										X	X	
Laboratory														
Hematology	X	X ^b			X	X	X	X	X	X	X	X	X	
Blood chemistry	X	X ^b			X	X	X	X	X	X	X	X	X	
Urinalysis	X	X ^b										X	X	X
HBV, HCV, HIV, HTLV-1	X													
EBV, CMV	X					X ^d	X ^d	X ^d	X ^d	X ^d	X ^d	X ^d	X ^d	
Pregnancy test ^c	X	X ^b					X		X		X	X	X	
Contraception check ^c	X	X ^b					X		X		X	X	X	
12-Lead ECG	X										X	X		
Chest X-ray	X													
Registration		X												
Study treatment														
Skin test		X												

	Screening period	Treatment period				Follow-up period								Follow-up of ET case
		Day 1 ^a (baseline)	Day 2	Day 3	Day 4	Day 8 Week 1	Day 15 Week 2	Day 29 Week 4	Day 43 Week 6	Day 57 Week 8	Day 71 Week 10	Day 85 Week 12	Day 169 Week 24 or ET	
Visit Identifier ^a	Screening													Follow up 28 days after ET
Visit Window	Day -28 to -1	N/A	N/A	N/A	N/A	±1 day	±1 day	±3 days	±3 days	±3 days	±3 days	±7 days	±7 days	+7 days
Investigational treatment administration		X	X	X	X									
Assessments														
Efficacy					X	X	X	X	X	X	X	X	X	
Safety		X	X	X	X	X	X	X	X	X	X	X	X	X
Concomitant treatment(s)	X	X	→	→	→	→	→	→	→	→	→	→	X	X
Serious and nonserious adverse event monitoring	X	→	→	→	→	→	→	→	→	→	→	→	X	X

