4. ANALYSIS SETS (POPULATIONS FOR ANALYSIS)

Data for all participants will be assessed to determine if participants meet the criteria for inclusion in each analysis population prior to releasing the database and classifications will be documented per standard operating procedures.

For purposes of analysis, the following analysis sets are defined:

Analysis Set	Description
Enrolled	“Enrolled” means a participant’s, or their legally authorized representative’s, agreement to participate in a clinical study following completion of the informed consent process. Potential participants who are screened for the purpose of determining eligibility for the study, but do not participate in the study, are not considered enrolled.
Full analysis set (FAS)	All participants assigned to investigational product and who take at least 1 dose of investigational product. For participants who discontinue study and/or receive blood transfusion or prohibited concomitant medication, any missing data will not be imputed and all observations after blood transfusion or prohibited concomitant medication will be included in the analysis.
Safety	All participants assigned to investigational product and who take at least 1 dose of investigational product.

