5.3. Methods to Manage Missing Data

For efficacy endpoints, observed values will be used at each designated visit without imputation for missing values.

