Appendix 2. Data Derivation Details

Appendix 2.1. Definition and Use of Visit Windows in Reporting

Visit windows in reporting are not defined in this study and the visit day for each value will be shown as necessary in the listings. No summary statistics will be reported.

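### SAP 3.2.3 derives transfusion independence from an absence of records without requiring follow-up to the closing visit, so a truncated participant can be labelled independent, chiefly at Week 24

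*SAP*

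**What the plan says.** Protocol 8.1.3 says only that transfusion independence is evaluated at Weeks 12 and 24. SAP Appendix 2.2 (Endpoint Derivations) is empty, so SAP 3.2.3 is the sole derivation.

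- **Week 12:** "Participants who do not have any transfusion records from the time of the first dose of the investigational product at Day 1" and onward "to the day of Week 12 visit (inclusive) will be regarded as transfusion independent at Week 12".
- **Week 24:** "Participants who do not have any transfusion records from the day after Week 12 visit to Week 24 visit (inclusive) will be regarded" as independent at Week 24.
- **Missing data (SAP 5.3):** "For efficacy endpoints, observed values will be used at each designated visit without imputation for missing values".
- **Full analysis set (SAP 4):** "For participants who discontinue study and/or receive blood transfusion or prohibited concomitant medication, any missing data will not be imputed". Participants who discontinue therefore stay in the set.
- **Visits:** the Schedule of Activities (Protocol 1.3) gives the last scheduled visit and early termination (ET) one column, "Day 169 Week 24 or ET". SAP Appendix 2.1 states that "Visit windows in reporting are not defined in this study".

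A footnote to SAP 3.2.3 deals with a Day 1 transfusion of unknown timing. It counts against independence at Week 12 and not at baseline. No rule covers follow-up that stops before the closing visit.

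**The concern.** The favourable label is what remains when no transfusion is recorded. Time that nobody observed cannot produce a transfusion record, so any gap in follow-up can move the label only towards 'independent'. The rule asks for no attendance at the closing visit, no documented follow-up up to it, and no survival to it.

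The no-imputation principle might be expected to catch this. It governs values that are missing at a visit. A programmer who applies SAP 3.2.3 as written obtains a complete value, 'independent', and never reaches the missing-data rule.

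The study has a target of three participants, no control arm and results listed participant by participant. The label in the listing is therefore the reported result for that endpoint, and a reader should be able to trust that 'independent' means followed and not transfused.

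**Working it through.** The plan has no figure to reproduce: the sample size is a feasibility target, with no alpha, power, effect size or dropout rate. The check applies the SAP 3.2.3 rule to hypothetical participants, with and without a follow-up requirement.

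**Inputs.** Week 12 is Day 85 and Week 24 is Day 169 (Protocol 1.3). On nominal days the Week 12 window is Days 1 to 85, which is 85 days. The Week 24 window is Days 86 to 169, and 169 − 86 + 1 = 84 days. Using nominal days is an assumption, because the SAP anchors the windows to visits.

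**Rules compared.** Literal rule: independent if no transfusion record falls in the window. With follow-up requirement: any record in the window gives 'not independent'; no record and follow-up to the end gives 'independent'; otherwise 'not evaluable'.

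| Hypothetical participant | Window | Days observed | Literal rule | With follow-up requirement |
|---|---|---|---|---|
| A. Transfused up to Day 80, attends Week 12, lost on Day 100 | Week 24 | 15 of 84 | independent | not evaluable |
| B. No transfusion recorded, lost on Day 40 | Week 12 | 40 of 85 | independent | not evaluable |
| B. Same participant | Week 24 | 0 of 84 | independent | not evaluable |
| C. Transfused on Days 5, 20, 40 and 55, died on Day 60 | Week 12 | 60 of 85 | not independent | not independent |
| C. Same participant | Week 24 | 0 of 84 | independent | not evaluable |
| D. Completer, last transfusion on Day 60 | Week 24 | 84 of 84 | independent | independent |

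Fractions observed: A, 15/84 = 18%; B at Week 12, 40/85 = 47%.

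**How firm each row is.** A at Week 24 and B at Week 12 have a window start that the SAP itself defines (the day after the Week 12 visit, and the first dose). Only the end is unobserved. B and C at Week 24 are weaker: without a Week 12 visit, that window has no start unless nominal days are substituted.

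**How often it could arise.** The documents give no dropout rate. If each participant independently leaves early with assumed probability d, the chance of at least one early departure among three is 1 − (1 − d)³:

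- d = 5%: 1 − 0.95³ = 14%
- d = 10%: 1 − 0.90³ = 27%
- d = 20%: 1 − 0.80³ = 49%
- d = 30%: 1 − 0.70³ = 66%

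These are chances of an early departure. A wrong label also needs a window with no recorded transfusion.

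**The case against.** **The windows end at visits.** If the Week 24 visit never happened, the window has no end. SAP 5.3 uses values observed at each designated visit, so the endpoint would be missing, not favourable. SAP 3.2.2 also extends evaluation to ET for the hematological test values only, which suggests that ET was not meant to stand in for Week 24 here. This reading is plausible and may be what the authors intended, but the SAP does not state it. The shared Week 24/ET column, the lack of reporting windows and the silence of SAP 3.2.3 on ET all leave room for the other reading.

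**The Week 12 label is less exposed.** Entry requires Stage 2b or above (Protocol 5.1), and Stages 2b and 3 are defined by red-cell transfusion need (Protocol Table 2). In the earlier randomised comparison with supportive care, daily platelet transfusions were needed during infusion (Protocol 2.2.3.1.1). One record after the first dose settles Week 12 as not independent. This stands: the exposure is mainly at Week 24.

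**Other listings reveal the truncation.** Survival status with date last known alive and any death (SAP 6.2.1.1), disposition with reason (SAP 6.4.2) and transfusions in 4-week intervals (SAP 6.4.4) are listed per participant. This also stands. It makes a wrong label detectable by cross-checking but leaves the label wrong.

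**Follow-up may continue after treatment stops.** Under Protocol 7.2, participants who ask to stop treatment remain in follow-up. Truncation would then come mainly from study withdrawal, loss or death, although Protocol 7.1 refers those who permanently discontinue the product to the ET and Follow-up visits.

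**Conclusion.** The point holds as a defect in a stated rule. As written, SAP 3.2.3 permits the label 'transfusion independent' for a participant not followed to the closing visit, and SAP 5.3 does not clearly prevent it. The clearest case is loss between Weeks 12 and 24, illustrated by 15 of 84 days observed. Cases that end before Week 12 depend on the nominal-day assumption.

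A reader might infer that the plan systematically reports loss or death as benefit, or that it biases an estimate by one third of the sample. The documents do not support that. No response rate, summary statistic or test is planned for this endpoint, so no estimate or error rate is affected. Three is a minimum, and one label is one of three listed results (one of four or five if more are enrolled). The visit-anchored reading would leave the value missing, and the favourable label arises only if that reading is not adopted.

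A reader might also infer that a death before the visit should count as 'not independent'. Nothing in the plan assigns that outcome. With no transfusion recorded in the window, it would also fill in unobserved time.

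The size is therefore a potentially misleading individual label on a listed secondary endpoint, partly detectable elsewhere. It is worth correcting because the correction is cheap.

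**What to change.** In SAP 3.2.3, for each window:

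1. Any recorded transfusion in the window gives 'not independent', whether or not the participant reached the closing visit.
2. 'Independent' requires documented transfusion follow-up through the Week 12 (or Week 24) visit and no transfusion recorded in the window.
3. All others are listed as 'not evaluable', with the last date of transfusion follow-up and the reason (death, withdrawal, lost). This includes a death before the visit with no transfusion recorded in the window.
4. An ET visit before the scheduled visit does not close the window.

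**Cost.** A few sentences in the SAP and additional listing fields for date and reason. Transfusions, disposition and date last known alive are already planned for listing. The endpoint is secondary, and both documents reserve a protocol amendment for major changes to the primary endpoint or its analysis, so a SAP revision should suffice. The downside is that some favourable labels may become 'not evaluable', which in a study this small could leave few evaluable results at Week 24.

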3.2.4. Survival status

During the study period, the survival status of each participant will be recorded.

3.3. Other Endpoint(s)

N/A.

3.4. Baseline Variables

No covariates and stratification variables are defined in this trial. The baseline variables to be listed are follows:

- Demographic characteristics.
- Details of aplastic anemia diagnosis (eg. Severity criteria of aplastic anemia, transfusion independence, prior rabbit-anti-thymocyte globulin [rabbit-ATG] treatment status).

3.5. Safety Endpoints

3.5.1. Adverse Events

MedDRA will be used to classify all AEs with respect to system organ class (SOC) and preferred term (PT). *The time period for actively eliciting and collecting AEs and SAEs (“active collection period”) for each participant begins from the time the participant provides informed consent, which is obtained before the participant’s participation in the study (ie, before undergoing any study-related procedure and/or receiving investigational product), through the last study visit (Week 24 visit or Follow-up visit of ET case).*

An adverse event is considered treatment emergent relative to a given treatment if the event started on or after Day 1 (start of PF-06462700 administration) and through the last study visit (Week 24 visit or Follow-up visit of ET case).

3.5.2. Laboratory Data

The following safety laboratory tests will be performed at times defined in the SoA section of this protocol. Additional laboratory results may be reported on these samples as a result of the method of analysis or the type of analyzer used by the clinical laboratory; or as derived from calculated values. These additional tests would not require additional collection of blood. Unscheduled clinical laboratory measurements may be obtained at any time during the study to assess any perceived safety concerns.

As described in SoA section of the protocol, *Hematology, Blood chemistry, Urinalysis, Coagulation, and Pregnancy test on Day 1 (baseline) can be omitted, if the interval between Screening visit and Day 1 visit is within 7 days.* In such cases, the values on screening visit will be used as baseline values.

Table 1. Protocol-Required Safety Laboratory Assessments

Hematology	Chemistry	Urinalysis	Other
Hemoglobin Hematocrit RBC count Reticulocyte count MCV MCH MCHC Platelet count WBC count Total neutrophils (Abs) Eosinophils (Abs) Monocytes (Abs) Basophils (Abs) Lymphocytes (Abs)	BUN Creatinine Glucose (fasting) Calcium Sodium Potassium Chloride AST, ALT Total bilirubin Alkaline phosphatase Uric acid Albumin Total protein	Glucose (qual) Protein (qual) Blood (qual)	At screening only: 
 • FSH^a • Pregnancy test (β-hCG)^b • Hepatitis B core antibody, surface antibody and surface antigen (HBV DNA if necessary) • Hepatitis C antibody (HCV RNA if antibody is positive) • HIV • HTLV-1 • EBV antibody (EBV DNA if antibody is positive and conduct at Week 2 and after) • CMV antibody (CMV DNA if antibody is positive and conduct at Week 2 and after)

Abbreviations: Abs = absolute; ALT = alanine aminotransferase; AST = aspartate aminotransferase; β -hCG = beta-human chorionic gonadotropin; BUN = blood urea nitrogen; CMV = cytomegalovirus; DNA = deoxyribonucleic acid; EBV = Epstein-Barr virus; FSH = follicle-stimulating hormone; HBV = hepatitis B virus, HCV = hepatitis C virus; HIV = human immunodeficiency virus; HTLV-1 = human T-cell leukemia virus type 1; MCH = mean corpuscular hemoglobin; MCHC = mean corpuscular hemoglobin concentration; MCV = mean corpuscular volume; qual = qualitative; RBC = red blood cell; RNA = ribonucleic acid; WBC = white blood cell.

a. For confirmation of postmenopausal status only.

b. Local urine testing will be standard for the protocol unless serum testing is required by local regulation or institutional review board/ethics committee (IRB/EC). Serum or urine β -hCG for female participants of childbearing potential.

3.5.3. Other Safety Endpoints

- SAEs and AEs leading to discontinuation;
- Vital signs.

4. ANALYSIS SETS (POPULATIONS FOR ANALYSIS)

Data for all participants will be assessed to determine if participants meet the criteria for inclusion in each analysis population prior to releasing the database and classifications will be documented per standard operating procedures.

For purposes of analysis, the following analysis sets are defined:

Analysis Set	Description
Enrolled	“Enrolled” means a participant’s, or their legally authorized representative’s, agreement to participate in a clinical study following completion of the informed consent process. Potential participants who are screened for the purpose of determining eligibility for the study, but do not participate in the study, are not considered enrolled.
Full analysis set (FAS)	All participants assigned to investigational product and who take at least 1 dose of investigational product. For participants who discontinue study and/or receive blood transfusion or prohibited concomitant medication, any missing data will not be imputed and all observations after blood transfusion or prohibited concomitant medication will be included in the analysis.
Safety	All participants assigned to investigational product and who take at least 1 dose of investigational product.

5. GENERAL METHODOLOGY AND CONVENTIONS

The primary analyses will be performed after study participant data set release after last participant last visit.

